### **6.15.3 Vital Signs, Height and Weight, and Other Safety Measures**

Vital signs will be summarized by presenting summary statistics of raw data and change from baseline values (means, medians, SD, ranges) for each visit (per analysis window) and time point. A data listing will include vital signs from all visits.

### **6.15.4 Electrocardiograms**

Incidence of the Investigator's overall assessment (normal, abnormal – not clinically significant, and abnormal – clinically significant) will be summarized.

### **6.15.5 Physical Examination**

New or worsening symptoms in the symptom-directed physical exams will be included in the by-subject data listing.

### **6.15.6 Analysis of Anti-Drug Antibody**

A data listing of anti-drug-antibodies (ADA) results will be provided for all subjects. Number (%) of subjects who are confirmed ADA-positive at any time after receiving study drug and number (%) of subjects who are confirmed ADA-positive at the end of study will be cross-tabulated by their ADA status and titers at predose.

## 7. Validation

Clinical Operations and Data Management at Allakos will work with the EDC/Data Management (DM) vendor to ensure that the data collected for the study are of the highest quality possible. The study monitor will be responsible for reviewing and verifying the accuracy of the data recorded on the electronic case report forms (eCRF) directly from source documents at the investigative site. The DM vendor will be responsible for performing edit checks and reviewing all data entered into the electronic database to identify discrepant and/or inconsistent values and to send queries to the clinical sites. The Investigator will be responsible for answering queries about discrepant data and providing electronic signatures to confirm data integrity.

The programming of tables, listings, and figures (TLF) based on the clinical data is outsourced. Allakos seeks to ensure the quality of the reports provided by the CRO in the form of TLF passing a rigorous validation process as follows:

- Derived datasets will be independently reprogrammed by a second programmer. The separate datasets produced by the 2 programmers must match 100%.
- Tables will be independently reprogrammed by a second programmer, and the results from both programs must match.
- Figures will be checked for consistency against corresponding tables and listings or independently reprogrammed if there are no corresponding tables or listings.
- Listings will be checked for consistency against corresponding tables, figures, and derived datasets.

All post hoc analysis, if accepted for inclusion in the study report, will follow the same quality process as stated above. The entire set of TLF will be checked for completeness and consistency prior to delivery to Allakos.

## 9. Appendices

- 9.1 Appendix 1: Dysphagia Symptom Questionnaire, CCI [REDACTED] and EoE Endoscopic Reference Score
- 9.2 Appendix 2: Intercurrent Events
- 9.3 Appendix 3: List of Tables, Listings, and Figures
- 9.4 Appendix 4: Example SAS Codes

**9.1 Appendix 1: Dysphagia Symptom Questionnaire, CCI [REDACTED], and EoE Endoscopic Reference Score**

**Dysphagia Symptom Questionnaire**

Patient ID: \_\_\_\_\_ - \_\_\_\_\_ - \_\_\_\_\_

Date: \_\_\_\_\_

**Dysphagia Symptom Questionnaire (DSQ)**

**Instructions**

This daily diary includes questions about your Eosinophilic Esophagitis (EoE). We are interested in any trouble you had today swallowing foods such as meat, rice, fruit, bread, etc.  
*Please complete this questionnaire after you have had your last meal of the day.*

Read each question and answer by selecting the box that best describes your experience. There are no right or wrong answers to any of the questions.

Question #1: During the past 24 hours, did you eat solid food?	 No  Yes
Question #2: During the past 24 hours, has food gone down slowly or been stuck in your throat?	 No  Yes
If you answered "Yes" to Questions 1 and 2, please proceed to answer Questions 3 and 4.	
Question #3: For the most difficult time you had swallowing food today (during the past 24 hours), did you have to do anything to make the food go down or to get relief?	 No, it got better or cleared up on its own  Yes, I had to drink liquid to get relief  Yes, I had to cough and/or gag to get relief  Yes, I had to vomit to get relief  Yes, I had to seek medical attention to get relief
Question #4: The following question concerns the amount of pain you have experienced when swallowing food:  What was the worst pain you had while swallowing food during the past 24 hours?	 None, I had no pain  Mild  Moderate  Severe  Very Severe

Allakos, Inc. Dysphagia Symptom Questionnaire v2.0

**9.1 Appendix 1 DSQ, [REDACTED], and EREFS cont.**

The DSQ was validated with the following scoring algorithm ([Hudgens, 2017](#)).

$$DSQ\ score = \frac{(sum\ of\ points\ from\ questions\ 2\ and\ 3\ from\ daily\ DSQ\ diary) \times 14\ days}{number\ of\ diary\ days\ reported\ with\ non-missing\ data}$$

CCI

CCI

CCI

CCI

CCI

## 9.1 Appendix 1 DSQ, EoEHSS, and EREFS cont.

### EoE Endoscopic Reference Score (EREFs)

(Hirano, 2013)

The EREFS is the sum of 5 components with a maximum score of 9 for each location (proximal and distal esophagus) and maximum combined score of 18. Individual component score ranges are as follows:

- Edema 0–1
- Rings 0–3
- Exudates 0–2
- Furrows 0–2
- Stricture Range 0–1

Each component is scored based on the presence and/or grade of each feature. Miscellaneous features will not be included in the total score.

Improvements in inflammatory and remodeling features may also be reported based on individual scores for edema, rings, furrows, exudate, and stricture.

Inflammatory and fibrostenotic subscores will be generated (proximal, distal, and combined). The inflammatory subscore is the sum of the exudate, edema, and furrows scores (range 0–5). The fibrostenotic subscore is the sum of the rings and stricture scores (range 0–4).

## 9.2 Appendix 2: Intercurrent Events

- A. Use of any of the following prohibited medications during the course of the study as described:
- 1) Immunosuppressive or immunomodulatory drugs (e.g., IL-5 modulators, i.e., benralizumab, reslizumab, mepolizumab; IL-4 and IL-13 antagonists, i.e., dupilumab; calcineurin inhibitors, i.e., cyclosporin, tacrolimus; mTOR inhibitors, i.e., sirolimus, everolimus; anti-metabolites, i.e., azathioprine, methotrexate, 6-mercaptopurine, leflunomide, mycophenolate mofetil; alkylating agents, i.e., cyclophosphamide; TNF inhibitors, i.e., infliximab, adalimumab; anti-IgE antibodies, i.e., omalizumab; and eosinophil depleting drugs, i.e., pramipexole).
    - a) Use at any point during the study.
  - 2) Glucocorticoids
    - a) Initiation of any course of treatment or single use of systemic or swallowed corticosteroids at a dose of  $>10$  mg/day of prednisone or equivalent starting at Week 21 and through the end of Week 24. This does not include use of corticosteroids given as pre-infusion prophylaxis or treatment of IRR.
- B. Use of restricted medications outside the protocol-defined specifications
- 1) Glucocorticoids
    - a) Discontinuation of a previously stable dose of systemic or swallowed corticosteroids ( $\leq 10$  mg/day of prednisone or equivalent) after the screening period.
    - b) Initiation of systemic or swallowed corticosteroids ( $\leq 10$  mg/day of prednisone or equivalent) following the screening period and continuing to at least Study Week 21 (within 2 weeks of efficacy assessment at Weeks 23 and 24).
  - 2) Proton Pump Inhibitors
    - a) Discontinuation of a previously stable dose of an oral PPI after the screening period and before the end of Week 24.
    - b) Initiation or increase in the dose of an oral PPI following the screening period and continuing to at least Study Week 21 (within 2 weeks of efficacy assessment at Weeks 23 and 24).

- 3) Sodium cromolyn
  - a) Discontinuation of a previously stable dose of sodium cromolyn after the screening period and before the end of Week 24.
  - b) Initiation or increase in the dose of sodium cromolyn following the screening period and continuing to at least Study Week 22 (within 1 week of efficacy assessment at Weeks 23 and 24).
- C. Any subject requiring a therapeutic EGD (defined as dilatation or other intervention for a narrowing or stricture) that may impact subsequent assessment of the DSQ during the first qualifying EGD at the end of the screening period or at any point during the study through Study Week 24.
- D. Discontinuation of Investigational Medical Product
  - 1) Discontinuation of study agent due to
    - a) Infusion-related reaction
    - b) Subject withdrawal
    - c) Meeting study withdrawal criteria (Protocol Section 13.10)

Per protocol, subjects are required to remain on stable doses of either PPI or corticosteroids ( $\leq 10$  mg of prednisone equivalent per day) throughout the course of the study if they are on a stable dose during the screening period. Because of the potential impact of corticosteroids and PPI on both histologic assessment of tissue eosinophil levels as well as patient-reported GI symptoms, subjects must meet the entry requirements for both histology and symptom burden (DSQ) if they are on any of these medications at screening, and therefore, must remain on a stable dose throughout the study in order to meaningfully interpret any change from baseline during the evaluation phase. Conversely, subjects starting these medications due to unforeseen medical necessity following the screening period and remaining on them through a time point sufficiently close to the evaluation period to potentially impact assessment of symptoms and/or histologic assessments will be considered as ICE. For PPI and corticosteroids ( $\leq 10$  mg/day of prednisone or equivalent), a conservative washout period is estimated at 2 weeks, and therefore, continuation of a new course of therapy beyond Week 21 could be considered as a potential ICE.

Sodium cromolyn is a mast cell stabilizer and could potentially impact reported symptoms in a similar way to one of the mechanisms of action of AK002. As such, discontinuation of a previously stable dose of sodium cromolyn after the screening period and before the end of Week 24 could be considered as a potential ICE. Likewise, the initiation or increase in the dose

of sodium cromolyn following the screening period and continuing to at least Study Week 22 (within 1 week of efficacy assessment at Weeks 23 and 24) could be considered as a potential ICE. It is estimated that 1 week would be a sufficient washout period for the effects of sodium cromolyn.

Antihistamines are unlikely to impact histologic assessments in the study but could have a slight impact in some symptoms depending on the type, dose, and duration of use. As such, subjects are required to stay on stable doses of antihistamines if they are taking them at the time of screening and to remain on them through completion of the study. Due to unforeseen medical circumstances and acknowledging that some patients may have concurrent allergic conditions, the use of these medications by some subjects during the study is anticipated.

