8.1 Prohibited Medications

Any biologics or medications that may interfere with the study, such as swallowed corticosteroids, systemic corticosteroids, and systemic immunosuppressive or immunomodulatory drugs (including azathioprine, JAK inhibitors, 6-mercaptopurine, methotrexate, cyclosporine, tacrolimus, anti-TNF, anti-IL-4 receptor (e.g., dupilumab), anti-IL-5 (e.g., mepolizumab), anti-IL-5 receptor (e.g., benralizumab), anti-IL-13 (e.g., lebrikizumab), anti-IgE (e.g., omalizumab), are prohibited for the duration of study participation.

The use of systemic or topical corticosteroids with a dose of >10 mg/day of prednisone or equivalent is prohibited unless it is due to unforeseen circumstances when it is deemed to be medically necessary to treat an unrelated medical condition or when given as a premedication prior to infusion or to treat an IRR that occurs during infusion. Any medications used for the treatment of IRR are not considered deviations from the protocol.

Subjects will be reminded to not take prohibited medications and to notify the site immediately if a prohibited medication is prescribed by another health care provider.

If medically necessary, rescue medications (systemic and/or swallowed topical corticosteroids) or emergency esophageal dilation may be used as rescue therapy. Any subject requiring rescue therapy must have an EGD (with biopsy collection and EREFS scoring) done prior to initiation

of rescue medications (or at the time of emergency esophageal dilation). The EGD performed due to initiation of rescue therapy will be used in place of the EGD scheduled for Day 169 (Week 24), and the subject will not have an EGD performed at the Day 169 (Week 24) visit. Subjects receiving rescue therapy should remain blinded, continue to receive study drug, and continue to comply with all study visits and assessments in accordance with the Schedule of Events (Table 1).

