#### **4.2.4 Intercurrent Events**

The events below are considered intercurrent events (ICE) confounding with the efficacy outcomes.

- Premature discontinuation from the study
- Use of prohibited/rescue medication
- Any therapeutic EGD (defined as dilatation or other intervention for a narrowing or stricture of the esophagus) at any point during the study through Week 24.

Further clarification and handling of ICE including prohibited/rescue medications is detailed in [Appendix 2](#).

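### SAP Appendix 2 flags a steroid course begun before Week 21 and still running then as an intercurrent event at ≤10 mg/day but not at >10 mg/day

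*SAP*

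**What the plan says.** SAP Appendix 2 itemises the ICEs. For corticosteroids above 10 mg/day of prednisone or equivalent, item A.2.a opens with the trigger, "Initiation of any course of treatment or single use of systemic or swallowed corticosteroids at a dose of" the stated level, and then sets the window: "of prednisone or equivalent starting at Week 21 and through the end of Week 24". Premedication and treatment of infusion reactions are exempt.

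At 10 mg/day or less, item B.1.b covers a start (at that dose "of prednisone or equivalent) following the screening period and continuing to at least Study Week 21"). The PPI item, B.2.b, has the same form: "Initiation or increase in the dose of an oral PPI following the screening period and continuing to at least Study Week 21". Item B.3.b does the same for sodium cromolyn, to Week 22.

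The Appendix 2 narrative gives the reason and counts as ICEs "subjects starting these medications due to unforeseen medical necessity following the screening period and remaining on them through a time point sufficiently close", where closeness is measured against the efficacy evaluation.

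The general wording is broader. SAP 4.2.4 lists use of prohibited or rescue medication with no dose or week limit, and then says: "Further clarification and handling of ICE including prohibited/rescue medications is detailed in"; the place it names is Appendix 2. Protocol 15.7.1 covers any prohibited or rescue start before the end of Week 24. Protocol 4.5.4 leaves the detail to the SAP, and SAP section 1 says that the SAP supersedes the protocol's statistical methods.

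**The concern.** A.2.a is triggered by a start inside a four-week window and has no continuation limb. The neighbouring items show that the authors wrote one when they wanted it. As itemised, the higher steroid dose gets the more lenient rule: a course from Week 15 to Week 24 is an ICE at 10 mg/day and not at 40 mg/day.

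Weeks 23–24 scores on such a course will exist, because Protocol 8.1 and 10.4 keep rescued subjects on study drug and in all assessments. Without an ICE those scores are analysed as observed, and steroid relief is credited to the randomised arm. That conflicts with the estimand question in SAP 4.2.5, which asks about outcomes without added medication that may affect the disease.

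The exposed endpoints are the DSQ co-primary, percent change in DSQ, >50% DSQ reduction, biweekly DSQ over time, and the DSQ part of the responder composite. They share the same scores, so this is one problem seen in several places. It matters most at the co-primary, because both co-primaries sit at step 1 of the high-dose testing order in SAP Table 7 and a DSQ failure there stops all later formal testing.

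Histology is protected after rescue, because Protocol 8.1 requires an EGD before rescue medication and uses it in place of the Day 169 one. It is not protected for the other route to >10 mg/day. Protocol 8.1 calls such use "prohibited unless it is due to unforeseen circumstances when it is deemed to be medically necessary to treat an unrelated medical condition", and no pre-steroid EGD is required in that case. SAP 5.4.1 removes counts only after an ICE, so Day 169 histology and EREFS could then be exposed too.

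**Working it through.** **Calendar.** SAP Table 2 counts study weeks in blocks of 7 days from Day 1. Week 21 is therefore Days 141–147, and Weeks 23–24 are Days 155–168.

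**The two rules on the same courses.** A.2.a is read as dose >10 mg/day and start in Weeks 21–24. B.1.b is read as dose ≤10 mg/day, start after screening, and end at Week 21 or later.

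| Course (study weeks) | ≤10 mg/day | >10 mg/day |
|---|---|---|
| 10–18 | no ICE | no ICE |
| 15–20 | no ICE | no ICE |
| 15–21 | ICE | **no ICE** |
| 15–24 | ICE | **no ICE** |
| 20–24 | ICE | **no ICE** |
| 21–24 | ICE | ICE |
| 23 only | ICE | ICE |

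The rules differ only for courses begun before Week 21 and still running at Week 21 or later. Item D does not close the gap: it covers stopping study drug for an infusion reaction, subject withdrawal or the Protocol 13.10 criteria, and none of these is steroid use. The sensitivity analyses in SAP 6.11.5 act only on scores on or after an ICE, so these scores stay as observed there as well.

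**The plan's own power.** Inputs from SAP 3.6 and 5.8: mean reductions of 15 and 7.5, so δ = 7.5; SD 15; 86 per arm; two-sided 0.05. For the two-sample t test the noncentrality is δ / (15 × √(2/86)). Power is 90.3% at 86 per arm and just under 90% (89.99%) at 85, so the stated 86 is reproduced.

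**Illustration for DSQ.** The documents give neither a rate of such courses nor a steroid effect; both are assumed. Let a fraction f of placebo subjects, and none on AK002, gain g points. Then δ = 7.5 − f × g.

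| f | δ, g = 7.5 | Power | δ, g = 3.75 | Power |
|---|---|---|---|---|
| 2% | 7.35 | 89.2% | 7.425 | 89.8% |
| 5% | 7.125 | 87.2% | 7.3125 | 88.9% |
| 10% | 6.75 | 83.5% | 7.125 | 87.2% |

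Allowing for the extra mixture variance on placebo lowers power by at most 0.4 points (83.1% instead of 83.5%).

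Reverse case, with use on AK002 only and g = 7.5: the difference moves 7.5 × f = 0.15, 0.375 or 0.75 points towards AK002. Equal use with equal gain leaves 7.5 unchanged.

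**Illustration for histology** (unrelated-condition use only). If every affected placebo subject became a responder, the placebo rate would be 0.10 + 0.90 × f = 11.8%, 14.5% or 19.0%. Exact Fisher power at 86 per arm against the SAP's 90% on AK002 stays above 99.9% in each case.

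**The case against.** The strongest reply is that the SAP body already treats these courses as ICEs. SAP 4.2.4 has no dose or week limit and presents Appendix 2 as clarification, not as a replacement list. SAP 4.2.5 opens from the premise that starting a prohibited medication at any time means withdrawal from study treatment, and draws the missing-data rule from it. The precedence statement ranks the SAP over the protocol, not an appendix over its own main text. Heading A also speaks of use, so the Week 21–24 phrase could be read as an exposure window.

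This stands in part: the intent is visible, and it is not certain that the data would be used as observed. It does not cure the defect. SAP 4.2.4 sends the handling of exactly these drugs to Appendix 2. The withdrawal premise in SAP 4.2.5 contradicts Protocol 8.1 and 10.4, and those passages must be reconciled in any case. The narrative's washout sentence is confined to PPI and doses of 10 mg/day or less. With two readings available, the co-primary dataset depends on an unstated choice.

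The second reply concerns size. The rates are assumed, and the power figures compare the gap with a fix that costs nothing. If the affected placebo subjects' information were wholly lost once set to missing, power would be 90.0%, 89.6% or 88.7% at 2%, 5% or 10%. The net gain from fixing is then about 1, 2 or 5 points with g = 7.5, and about 0.3, 0.7 or 1.5 points with g = 3.75. That is fair, and it shows that the likely effect is modest.

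The safeguards cited are partial. Prohibited-medication use is listed and a Per Protocol DSQ analysis is planned, but its exclusions are not yet specified (SAP 6.1.4) and it is supplementary.

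**Conclusion.** The concern holds. As itemised, Appendix 2 classifies the same ongoing steroid course as an ICE at the lower dose and not at the higher one, and the broader text conflicts with that list without settling it. This should be fixed, but it is not fatal. No sample-size figure is wrong.

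The size is unknown, because it depends on how many such courses occur, in which arm, and how much they relieve dysphagia. On the assumptions shown, use by 2–10% of placebo subjects alone takes 0.15–0.75 points off the 7.5-point DSQ difference if the gain is 7.5 points, and about half that if it is 3.75. More use on placebo shrinks the difference; more on AK002 inflates it. The first co-primary conclusion is safe on the SAP's response rates. No estimate was made for EREFS. Dilation is outside this point, since item C already makes it an ICE.

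**What to change.** Before unblinding, extend A.2.a so that systemic or swallowed corticosteroid use above 10 mg/day, begun or raised above that level after the first dose and for any indication, is an ICE if it is ongoing at Week 21 or begins from Week 21 through the end of Week 24. Keep the exemption for premedication and infusion reactions. State that the ICE dates from the start of the course. Align SAP 4.2.4 and the Appendix 2 narrative with this line, and say in the SAP how the rule departs from Protocol 15.7.1 for courses that end before Week 21.

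The cost is one clause and some matching wording. It needs no new data and no protocol amendment, because the SAP supersedes the protocol's statistical methods. The downside is that a few more subjects are flagged, with later continuous data imputed and binary outcomes counted as non-response. The change concerns analysis classification only and takes no position on steroid dose, rescue or patient care.

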15.7.1 Primary Efficacy Endpoint Analysis

The first co-primary endpoint is the proportion of subjects who achieve a peak esophageal intraepithelial count of ≤ 6 eosinophils/hpf at Week 24. The endpoint will be analyzed using Fisher's exact test comparing the AK002 group and placebo group for the proportion of treatment responders. Subjects who experience an ICE (e.g., exit the study prematurely or initiate prohibited/rescue medication or therapeutic EGD procedure) prior to the end of Week 24 will be treated as non-responders.

The second co-primary endpoint is the mean change in DSQ score from Baseline to Weeks 23-24. The DSQ score will be analyzed using ANCOVA with treatment as a factor, and Baseline DSQ and age strata (12-17, ≥ 18) as covariates. The Baseline DSQ will be calculated using the DSQ scoring algorithm for all daily DSQ assessments collected during the 2 weeks prior to the first infusion of study drug.

Data on subjects who experience an ICE (e.g., exit the study prematurely or initiate prohibited/rescue medication or therapeutic EGD procedure) prior to the end of Week 24 will be set to missing. Missing DSQ will be imputed using the Markov Chain Monte Carlo (MCMC) method.

Two sensitivity analyses will be conducted for the second co-primary endpoint. The first sensitivity analysis will be based on the placebo-based pattern-mixture model for the missing data imputation under the missing not at random (MNAR) assumption. In this model, subjects from the active treatment group after the ICE are assumed to behave like the subjects from the placebo group. Their missing data are imputed using the response profile from the placebo subjects who have similar baseline covariates and prior response trajectory. The second sensitivity analysis will utilize the tipping point method. In this method, the missing biweekly DSQ will be imputed with different adjustments for the active treatment subjects and placebo subjects under the MNAR assumption in search for a tipping point that reverses the study conclusion (i.e., p-value no longer < 0.05 for the treatment effect).

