#### **4.2.5 Strategy for Handling Intercurrent Events**

Per the study protocol, if a prohibited medication is started during the course of the study, the subject will be withdrawn from study treatment and followed for the 12-week follow-up period. In addition, the follow-up EGD may not be performed. Thus, for analysis of the trial product estimand, tissue eosinophil values and DSQ scores will be counted as non-responders for binary variables and set to missing for continuous outcomes from the point when an ICE occurs. An appropriate method for handling missing data through statistical modeling (e.g., multiple imputation [MI]) will be used (Sections [5.4.1](#), [5.4.2](#), and [6.11](#)). The estimand will provide an answer to the question that is crucial to individual subjects:

“If I take this study drug as part of my treatment regimen, without adding any further medications or the use of therapeutic endoscopic interventions that may impact the underlying disease or exit the study prematurely, what improvements in histology and PRO symptoms might be anticipated after 24 weeks?”

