### 5.4 Handling of Dropouts, Missing Data, and Data Discrepancies

#### 5.4.1 Missing Tissue Eosinophil Count at Week 24

Eosinophil counts will be set to missing if they are collected after subjects have experienced ICE. Subject with missing Week 24 tissue eosinophil count for any reason will be imputed with the eosinophil count collected from the post-baseline unscheduled visit prior to missing. If no eosinophil count is collected post-baseline, the subject will be considered treatment failure for tissue eosinophil response.

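### SAP Appendix 2 counts corticosteroids above 10 mg/day as an intercurrent event only from Week 21, so DSQ scores after earlier steroid rescue are analysed as observed, contrary to Protocol 15.7.1 and the SAP's own estimand

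*SAP*

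**What the plan says.** **Protocol 15.7.1.** For the first co-primary endpoint, subjects who "initiate prohibited/rescue medication or therapeutic EGD procedure) prior to the end of Week 24 will be treated as non-responders". For the second, their DSQ data are set to missing and imputed.

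**SAP 4.2.4.** The list of ICEs includes "Use of prohibited/rescue medication" with no time limit and leaves the detail to Appendix 2. The time phrase in that list belongs to the therapeutic EGD entry, not to medication. SAP section 1 says that the SAP supersedes the protocol's statistical methods, so Appendix 2 is the operative rule.

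**SAP Appendix 2.**
- A.1: immunosuppressive and immunomodulatory drugs count at any point in the study.
- A.2.a: corticosteroids above 10 mg/day count on initiation or single use at a dose "of prednisone or equivalent starting at Week 21 and through the end of Week 24", excluding premedication and treatment of infusion reactions.
- B.1.b: corticosteroids at or below 10 mg/day count when started "following the screening period and continuing to at least Study Week 21".
- C: therapeutic EGD counts at any point through Week 24.

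**Conduct after rescue.** Protocol 8.1 names systemic and swallowed topical corticosteroids as the rescue medication and says: "Subjects receiving rescue therapy should remain blinded, continue to receive study drug, and continue to comply with all study visits". It requires an EGD before the steroid is started, uses it in place of the Day 169 EGD, and omits the latter. SAP 4.2.5 instead says that "if a prohibited medication is started during the course of the study, the subject will be withdrawn from study treatment".

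**Missing histology.** Under SAP 5.4.1, a missing Week 24 count is "imputed with the eosinophil count collected from the post-baseline unscheduled visit prior to missing". Only subjects with no post-baseline count are treated as failures.

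**The concern.** A subject who needs high-dose steroid rescue at Week 12 has, under the protocol, an ICE. Under Appendix 2 the same subject has none. Protocol 8.1 keeps that subject on study drug and on the daily diary, so the DSQ keeps being collected under steroid. SAP 5.4.2 removes only scores collected after an ICE, so these scores stay in the primary ANCOVA.

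SAP 4.2.5 asks what improvement is expected without adding further medications. The estimate for the second co-primary endpoint would then partly answer a different question. The composite responder endpoint (more than 30% DSQ reduction plus histology) and the more-than-50% DSQ endpoint are affected in the same way, and both sit in the alpha-controlled hierarchy of SAP 5.8.

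**Working it through.** **1. Does another item in Appendix 2 catch early high-dose rescue?** Take a course above 10 mg/day started at Week 12.

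| Item | Applies? | Reason |
|---|---|---|
| A.1 | No | Lists other drug classes, not corticosteroids |
| A.2.a | No, as written | The start is before Week 21 |
| B.1.a, B.1.b | No | Limited to 10 mg/day or less |
| C | No | No dilation or other intervention |
| D | No | Study drug continues under Protocol 8.1 |

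The same dates at 10 mg/day or less, continued to Week 21, would be an ICE under B.1.b. The rule is thus inverted by dose. Emergency dilation at Week 12 is also an ICE (item C), although Protocol 8.1 names dilation and steroids together as rescue therapy.

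If single use is read to include each dose of an ongoing course, a course still running at Week 21 is caught. Rescue completed before Week 21 still is not, which remains narrower than Protocol 15.7.1.

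**2. Do the sensitivity analyses cover it?** Both analyses in SAP 6.11.5 start by setting to missing the biweekly DSQ derived from scores on or after an ICE. Scores never flagged as post-ICE are neither removed nor shifted.

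**3. The plan's own figure.** Inputs from Protocol 15.2 and SAP 3.6: difference 15 − 7.5 = 7.5, SD 15, 86 per group; two-sided alpha 0.05 from SAP 5.8.
- SE = 15 × √(2/86) = 2.29.
- Two-sample t power is 0.8999 at 85 per group and 0.903 at 86, so 86 reproduces.
- 86/(1 − 0.14) = 100 per group reproduces.

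These figures do not depend on the ICE window.

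**4. Size of the effect on DSQ.** The documents give no rescue rates, so the following are assumptions. Let f be the share of an arm with early steroid use, and g the gain in points (extra DSQ reduction) on steroid compared with no rescue. SD is held at 15.

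Difference = 7.5 − f_pbo × g_pbo + f_act × g_act

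| f placebo | f active | g placebo | g active | Difference | Power at 86 per group |
|---|---|---|---|---|---|
| 5% | 5% | equal | equal | 7.5 | 0.903 |
| 10% | 5% | 7.5 | 7.5 | 7.5 − 0.75 + 0.375 = 7.125 | 0.872 |
| 5% | 5% | 15 | 0 | 7.5 − 0.75 = 6.75 | 0.835 |
| 10% | 0% | 15 | – | 7.5 − 1.5 = 6.0 | 0.742 |
| 0% | 10% | – | 15 | 7.5 + 1.5 = 9.0 | 0.97 |

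With f from 0 to 10% and g from 0 to 15, the difference therefore ranges from 6.0 to 9.0.

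**5. Histology.** When Protocol 8.1 is followed, the biopsy used for Week 24 precedes the steroid. If early rescue were an ICE, SAP 5.4.1 would still use that same pre-rescue count. A rescued subject with 6 or fewer eosinophils/hpf on that biopsy would therefore count as a responder whichever way A.2.a is worded. That conflicts with the non-responder rule in Protocol 15.7.1 and SAP 4.2.5. Each such subject is worth 1 percentage point at 100 per arm.

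**The case against.** **A time limit may be deliberate.** Protocol 4.5.4 leaves the detailed handling of ICEs to the SAP, and Protocol 15.1 lets the SAP modify the methods. Appendix 2 reasons from closeness to the evaluation period. Protocol 8.1 also allows doses above 10 mg/day for unrelated medical necessity, so A.2.a covers more than rescue for EoE. This stands in part: whether a short, unrelated course finished well before Week 21 should count is a clinical judgement, and the fix leaves it exempt. It does not justify the wording as it is. The stated two-week washout covers only PPI and doses of 10 mg/day or less, and it cannot explain exempting a course still running at Weeks 23–24.

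**The appendix may intend to catch ongoing courses.** Its rationale says that subjects who start these medications after screening and stay on them close to evaluation will be ICEs. In context this refers to PPI and low-dose steroids. The following text weakens it: "continuation of a new course of therapy beyond Week 21 could be considered as a potential ICE". The intent is plausible, but the rule does not state it.

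**SAP 4.2.5 has some protocol support.** Protocol 14.2 lists use of a non-permitted drug without Medical Monitor approval as a possible reason to stop treatment. That is true, but it does not describe rescue, which Protocol 8.1 permits with study drug continuing.

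**The cases would be visible.** Prohibited medication is a deviation category and has its own listing, and a per-protocol DSQ table is planned. That helps a reader find the cases. It does not correct the primary analysis, and the per-protocol exclusions are not yet specified.

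**A stronger reading on histology.** A reader might infer that steroid-treated biopsies contaminate the first co-primary endpoint as well. The documents do not support this: under Protocol 8.1 the biopsy comes before the steroid and the Day 169 EGD is not done. An on-steroid Day 169 biopsy could arise only if the rescue EGD were missed or the steroid were given for another condition.

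**Conclusion.** The point holds for DSQ. As written, A.2.a is narrower than Protocol 15.7.1 and SAP 4.2.4 and inconsistent with B.1.b. It leaves DSQ after early high-dose steroid rescue in the second co-primary analysis and the DSQ-based responder endpoints as observed, outside both missing-not-at-random analyses.

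Neither size nor direction can be known from the documents. More rescue on placebo dilutes the effect, more on active inflates it, and equal use with equal gain cancels. The limit of 1.5 points rests on the assumed 0–10% use and 0–15 point gain. The 15-point gain is a corner case, since it equals the whole reduction assumed for the active arm, and a course completed early may leave little residual effect. A reader might take the 74% power figure as an expected loss; it is one end of an assumed range.

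The histology problem is separate. It comes from SAP 5.4.1 conflicting with the non-responder rule, and changing A.2.a alone would not resolve it. At the planned 90% against 10% response it would not alter significance: setting 10% of responders in each arm to non-response gives 81/100 against 9/100, Fisher p < 0.0001.

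This should be corrected before unblinding.

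**What to change.** 1. **Appendix 2, A.2.a.** Define as an ICE (i) any systemic or swallowed topical corticosteroid given as rescue under Protocol 8.1, from first dose to the end of Week 24; and (ii) any other course above 10 mg/day prednisone equivalent that starts from Week 21 or continues to at least Week 21, in line with B.1.b. Keep the exclusions for premedication and infusion reactions. If exempting rescue completed before Week 21 is intended, say so and give the reason for departing from Protocol 15.7.1.
2. **Appendix 2 rationale.** Replace the permissive wording about potential ICEs with a definite rule.
3. **SAP 4.2.5.** Correct the statement that these subjects are withdrawn from treatment so that it matches Protocol 8.1.
4. **SAP 5.4.1.** State that subjects with an ICE are non-responders for the binary histology endpoints only. Keep the pre-rescue count for percent change in eosinophils, since Protocol 8.1 designates that biopsy as the Week 24 one.

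The cost is SAP wording and the ICE and responder derivations, before unblinding. No new data are needed, and the estimand and testing hierarchy do not change. The downside is somewhat more imputed DSQ values and more subjects counted as non-responders.
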